6.4 Participant Follow-Up

6.4.1 Follow-Up Intervals and Methods

All participants are to be followed according to the investigational site's SOC practices. In addition to the SOC visits, treated participants will have an investigation follow-up visit at 30-days and 6-weeks as well as 6- and 12-months post index procedure and will have a phone call follow-up at 3-, 18- and 24-months. For participants into whom the WavelinQTM EndoAVF System was introduced during the index procedure but procedure success was not achieved, only the follow up at 30-days will be completed and limited to the collection of safety events and interventions. This follow-up may be conducted by phone for these participants and investigation participation for these participants will end upon completion of this follow-up.

All follow-up must be performed by authorized delegated clinical investigation site team members. Follow-up windows will be calculated from the index procedure date. Refer to Section 1.3 for an overview of follow-up window time frames and requirements for each visit. The following data will be collected and documented on the appropriate eCRF for each follow-up unless otherwise specified for treated participants:

- DUS: A DUS assessment per the Ultrasound Guidelines must be performed at the follow-up visits at 30-days and 6-weeks for all treated participants and again at 6-and 12-months for participants not yet successfully dialyzing with the AVF created as part of this clinical investigation using 2-needle cannulation. The 6- and 12-month DUS are also required for participants that are using the AVF created as part of this clinical investigation but for whom procedure access was obtained at the wrist artery during the index procedure. The DUS for these participants will be limited to the examinations of the artery that was accessed during the index procedure. At minimum, images including the following characteristics are required and must be submitted to the Sponsor / Core Lab as per the details specified in the investigational site's regulatory binder:
 - o Arteries and veins of the AVF: Patency (including characterization of each stenosis, if present), and inner diameters. Brachial artery volume flow.
 - AV-anastomosis & juxta-anastomotic area: Patency (including characterization of each stenosis, if present).
 - o Cannulation veins: Patency (including characterization of each stenosis, if present) and inner diameters.
 - o Perforator vein: Patency (including characterization of each stenosis, if present), as well as inner diameter and length.
 - Procedure access wrist artery (if used during index procedure): Patency (including characterization of each stenosis, if present), confirmation of flow, and inner diameter.

- Clinical Exam: Overall health and assessment of AV access function must be evaluated and documented with a physical exam conducted by the PI or authorized designee in accordance with each investigational site's SOC.
- *HD History and Status*: Determine and document if and how the participant has been and / or is receiving HD (AVF, CVC, etc.), and document the date of the participant's last HD session. Once HD (1- or 2-needle cannulation) is initiated via the AVF created as part of this investigation, HD details must be documented and detailed HD access data (e.g., cannulation logs) will be provided to the Sponsor or designee for review and analysis as follows:
 - Obetailed HD access data will be collected to indicate whether the participant successfully dialyzes with 2-needle AVF cannulation for at least 75% of HD sessions for three (3) continuous weeks and / or within 28 consecutive days. For the functional maturation and functional HD usability assessments, source documentation indicating HD success and vascular access used will be documented and collected until the endpoints are met (Sponsor verification is required before the clinical investigational site may stop collecting this HD access information).
 - O Thereafter determine and document if and how the participant has been and / or is receiving HD and whether the participant continues to be successfully dialyzed through the index AVF (the AVF created as part of the index procedure of this investigation) and document the date of the participant's last HD session.
- *SF-VAQ and EQ-5D Surveys:* Surveys will be completed by the participant or verbally read and documented by an authorized delegated investigation site team member for completion during the 6-week as well as 6-, 12- and 24-month followups.
- Documentation of AEs: Documentation of occurrence and / or status of AEs since the last follow up (refer to Section 8).
- Documentation of Interventions: Any access circuit interventions the participant has undergone since the index procedure and / or prior follow-up.

If the participant is treated by a health-care professional other than the PI for treatment related complications during the course of the follow-up period, the PI or authorized designee must request copies of the medical records and, if necessary, complete the appropriate eCRFs.

6.4.2 Unscheduled Follow-Up

An unscheduled visit follow-up eCRF should also be completed for participants who return for additional non-investigation scheduled follow-up examinations pertaining to their HD vascular access. The participant will be required to return for the next scheduled follow-up visit if the unscheduled visit is out of the CIP allotted follow-up window or if the required elements of the respective follow-up were not completed as part of the unscheduled visit (e.g. DUS, SF-VAQ and EQ-5D Surveys, etc.). Assessments completed and information obtained during an unscheduled visit may include:

- Clinical Exam: Overall health and assessment of AV access function should be evaluated and documented with a physical exam in accordance with each investigational site's SOC.
- *HD History and Status:* Determine and document if and how the participant has been and / or is receiving HD (AVF, CVC, etc.). Refer to Section 6.4.1 for HD data to be collected.
- Documentation of AEs: Documentation of occurrence and / or status of AEs since the last follow up (refer to Section 8).
- Documentation of Interventions: Any access circuit interventions the participant has undergone since the index procedure and / or prior follow-up.

If the participant is treated by a health-care professional other than the PI for treatment related complications during the course of the follow-up period, the PI or authorized designee should request copies of the medical records and, if necessary, complete the appropriate eCRFs.

6.5 Participant Investigation Completion and Premature Discontinuation

Following the index procedure, every participant into whom the WavelinQTM EndoAVF System was introduced should remain in the clinical investigation until completion of the required follow-up period. The follow-up period for this clinical investigation is 24 months $(730 \pm 30 \text{ days})$ for treated participants and 30 days (\pm 5 days) for participants into whom the WavelinQTM EndoAVF System was introduced during the index procedure but procedure success was not achieved. A treated participant is considered to have completed the investigation if the participant has completed the formal follow-up period associated with this clinical investigation through the 24-Month follow-up as described in the Schedule of Activities (Section 1.3).

However; a participant's participation may be prematurely discontinued. Additional participants will not be enrolled to replace those who withdraw from the clinical

investigation. Potential reasons for discontinuation may include, but are not limited to the following:

- Withdrawn Consent: The participant may at any time request to discontinue their participation in the clinical investigation. The PI must attempt to identify and document the reasons for discontinuation. If the participant withdraws consent for disclosure of future information, the Sponsor may retain and continue to use any data collected before such a withdrawal of consent.
- Withdrawal by PI: Participation may be immediately discontinued by the PI if, in the opinion of the PI, the participant would be exposed to inappropriate risk by continuing in the clinical investigation. Additionally, the PI may discontinue a participant's participation with prior written approval from the Sponsor if the participant is repeatedly noncompliant with clinical investigation procedures.
- Lost to Follow-Up (LTF): A participant may be considered LTF if the investigation site team members are unable to locate the participant despite three documented attempts to notify the participant via telephone and, if necessary, a certified letter to the participant's last known mailing address or local equivalent methods. This does not apply to missed visits, where the participant misses one of the follow up contact time points but completed a subsequent one (when participant misses two consecutive follow-ups and is unable to be contacted with the documented attempts outlined before, the participant may be considered LTF and withdrawn from the clinical investigation). The site should also contact the HD center to ascertain the participant's status. Before the site considers a participant LTF, written agreement should be obtained from the Sponsor.
- Participant Death: The participant becomes deceased. If known, the cause of death must be documented and an AE eCRF must be completed.
- *Clinical Investigation Termination:* The clinical investigation is terminated by the Sponsor (see Section 12.9).

Upon investigation completion or premature discontinuation (in the situations where applicable), the participant's continued care should be administered per SOC at the discretion of the PI and / or their primary care physician.

7 STATISTICAL METHODS

This section includes a summary of the planned statistical analyses and an overview of the statistical methods. The Statistical Analysis Plan (SAP) will be finalized prior to Database Lock and will include the technical and detailed descriptions of the statistical analyses summarized herein.

7.1 Overview of Clinical Investigation Design

This clinical investigation will be a global, multi-center, prospective, post-market, confirmatory, interventional, non-randomized, single arm clinical investigation to further evaluate the safety and effectiveness of the WavelinQTM EndoAVF System for endovascular fistula creations in the ulnar and radial vessels when accessed from the wrist (and / or upper arm) arteries and concomitant veins in the parallel or anti-parallel configuration.

7.2 Analysis Populations

The analysis populations will be defined as follows:

- The ITT population will consist of all participants into whom the WavelinQTM Endovascular System was introduced including those in whom procedure success was not achieved.
- An As-Treated (AT) population will include all treated participants, which includes all ITT participants but excludes those into whom the WavelinQTM Endovascular System was introduced but procedure success was not achieved.
 - The AT population is composed of two subpopulations: The incident population and the prevalent population as defined in Section 4.5.2.
- A Per-Protocol (PP) population may be created if there are participants who have any major deviations. The PP population will consist of any participants in the AT population who do not have any major deviations. The deviations that are considered to have a "major" grade will be defined a priori in the SAP.

All effectiveness endpoints will be analyzed primarily based on the AT population. All safety endpoints will be analyzed primarily based on the ITT population. PP analyses may also be performed for the primary endpoints. They will only serve as sensitivity analyses for the primary analyses.

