3 CLINICAL INVESTIGATION DESIGN

This is a global, multi-center, prospective, post-market, confirmatory, interventional, non-randomized, single-arm, clinical investigation to further demonstrate the safety and effectiveness of the WavelinQTM EndoAVF System for endovascular fistula creations in the ulnar and radial vessels when accessed from the wrist (and / or upper arm) arteries and concomitant veins in the parallel or anti-parallel configuration.

Safety objective: The safety outcome of participants receiving treatment with the WavelinQTM EndoAVF System will be compared to a Performance Goal (PG) derived from the prior clinical investigations evaluating the WavelinQTM EndoAVF System to confirm that the safety profile of the device is maintained.

Effectiveness objectives: The effectiveness measure evaluated through the primary effectiveness endpoint will be used to assess the performance of the WavelinQTM EndoAVF System when used in the creation of AVFs in a post-market fashion. The clinical investigation will aim to evaluate the number of interventions per patient year (PY) to facilitate (facilitation interventions) and maintain (maintenance interventions) use of the AVF and compare this to clinical guideline recommendations. Non-hypothesis tested secondary endpoints will evaluate the performance of the endovascularly created AVFs with respects to short-term (maturation / cannulation) and long-term (functional cumulative patency) performance characteristics.

A total of approximately one-hundred and fifty (150) treated participants will be included. Note that as per the definition of treated participant (refer to Section 6.2), this number does not include the participants into whom the WavelinQTM EndoAVF System was introduced but in whom procedure success (as defined in Section 4.3) was not achieved (estimated to total approximately ten [10] participants).

Under the current enrollment assumptions, a target of approximately 15 investigational sites (up to a maximum of 30 investigational sites) may participate globally. This investigation will enroll participants who are either already receiving HD at the time of screening (prevalent participants), regardless of access type (CVC, AVF, and / or AVG), or those who are not yet receiving HD but are in need of a vascular access as determined by the referring clinician (incident participants).

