7.5 Secondary Endpoints

The secondary endpoints will be summarized with descriptive statistics (without formal statistical hypothesis testing) using the ITT population for the safety endpoints and the AT population for the effectiveness endpoints. For time-to-event endpoints, the KM production limit method will be used to determine the rate. For categorical variables, summary statistics will include frequency counts and percentages. For rate variables, summary statistics including number of event / PY. For continuous variables, summary statistics will include mean, standard deviation, minimum, median, and maximum. CIs (95%) will be provided using appropriate assumptions based on the variable type. Refer to Section 4.2 for any applicable definitions.

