- Otherwise, if the participant did not achieve physiological maturation and has passed the specific visit
  window by the cutoff date of database lock, the participant is considered as not having an event. If the
  participant had access permanent abandonment prior to achieving physiological maturation and has passed
  the specific visit window by the cutoff date of database lock, the participant is considered as not having an
  event.

This endpoint will be evaluated on the AT population. The proportion of physiological maturation and the 95% two-sided CI will be provided using the Clopper-Pearson method. For the 6-month reporting, the physiological maturation rate up to 6-months (up to Day 210) will be presented. For the final reporting, the physiological maturation rate up to 24-months (up to Day 760) will be presented.

Similar analysis will be done for exploratory purposes, for physiological maturation defined as an AVF having at least 500 mL / min of flow in the brachial artery and an outflow vein diameter of  $\geq$  5 mm as measured by DUS.

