#### 5.2.3 Cannulation Success

Cannulation success is defined as with successful first use for HD using 2-needle cannulation. This endpoint will be evaluated through 6 months. Additionally, for exploratory purposes, the endpoint will be evaluated through 30 days, 6 weeks, 3 months, 12 months, 18 months, and 24 months.

The event of cannulation success will be identified if:

On the EndoAVF Dialysis page, "Date endoAVF First Used with 2 Needles for Hemodialysis" is not NULL and within a specific visit (e.g., within 210 days for 6 months post creation).

Kaplan-Meier (KM) analysis will be used to estimate the time from HD AV access creation (the date of index procedure) to first successful use for HD using 2-needle cannulation through certain post creation visit.

- If cannulation success occurs, the participant is considered as having the event at the corresponding date.
- If the participant was transferred to PDs, or had a kidney transplant, or had access discontinuation, or discontinued before the end of a specific visit window (e.g.180+30 = Day 210 for 6-month visit) without cannulation success, the participant is considered as censored at the earliest date among these events (i.e. PD start date, kidney transplant date, date of access discontinuation, or last date of available study data including the unscheduled visit date).
- Otherwise, if the participant did not achieve cannulation success and has passed the specific visit window by the cutoff date of database lock, the participant will be censored at the end of the reporting time window (e.g., 180+30 = Day 210 for the 6-month reporting, 730+30 = 760 for the 24-month reporting) for this analysis. If the participant had access permanent abandonment prior to achieving cannulation success and has passed the specific visit window by the cutoff date of database lock, the participant will be censored at the date of permanent abandonment.

This endpoint will be evaluated on the AT population. The number of participants with events, number of participants censored, time to event (days), and proportion of participants with events along with the 95% CI will be presented at 6-months post creation using the KM method. For the 6-month reporting, the cannulation success rate up to 6-months (up to Day 210) will be presented. For the final reporting, the cannulation success rate up to 24-months (up to Day 760) will be presented.

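### Maturation and cannulation success are planned only among participants whose procedure succeeded; a supportive ITT result that counts procedure failures should be added

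*Protocol*

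**What the plan says.** Protocol 7.2 and SAP 4.1 define ITT as everyone into whom the system was introduced. AT is the ITT set less the procedure failures: it "excludes those into whom the WavelinQTM Endovascular System was introduced but procedure success was not achieved". Protocol 7.2 then rules: "All effectiveness endpoints will be analyzed primarily based on the AT population". Protocol 7.5 repeats the split for the secondary endpoints, "using the ITT population for the safety endpoints and the AT population for the effectiveness endpoints".

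The SAP follows this. For physiological maturation, section 5.2.2 says: "This endpoint will be evaluated on the AT population. The proportion of physiological maturation" is then given with a Clopper-Pearson interval. For cannulation success, a Kaplan-Meier analysis, section 5.2.3 says: "This endpoint will be evaluated on the AT population. The number of participants with events" and the related summaries follow. Neither section names an ITT version.

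On numbers, Protocol section 3 plans that "A total of approximately one-hundred and fifty (150) treated participants will be included", and adds that this excludes participants in whom procedure success "was not achieved (estimated to total approximately ten [10] participants". Those participants leave the study after a 30-day contact for safety and interventions (Protocol 6.4.1). Procedure success itself is analysed on ITT (SAP 5.3.1), but as an exploratory endpoint, and Protocol 7.6 makes presentation of exploratory endpoints optional.

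**The concern.** The effectiveness objective in the protocol synopsis is that the device produces a fistula usable for hemodialysis. A procedure that creates no fistula is the plainest failure of that objective, yet AT membership depends on creation having succeeded, which is itself an outcome of the device. Removing these participants can only raise a success proportion.

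They are not missing data. With no index fistula there is nothing to mature or cannulate, so their outcome on both endpoints is known at the index procedure, and the short follow-up does not stand in the way of counting them. SAP 5.2.2 already applies this reasoning to a later failure: a fistula permanently abandoned before maturing stays in the denominator as a non-event, whereas one never created drops out.

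At stake is how the descriptive rates will be read. They are the main planned evidence on maturation and first use, and a reader may take them as the chance of a usable fistula when the device is tried.

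**Working it through.** **Inputs**
- AT participants: 150 (Protocol section 3).
- Procedure failures F: about 10 (Protocol section 3). No derivation is given, so the figure cannot be reproduced; it implies procedure success of 150/160 = 93.75%.
- Pre-market procedure success: 88/91 = 96.7% (Protocol 2.1.2). At that rate F = 150/(88/91) − 150 = 5.1. The exact 95% interval for 88/91 is 90.7% to 99.3%, which gives F from about 1 to about 15.
- Illustrative AT rates: 60%, 70% and 84.9%. The last is the pre-market 6-month Kaplan-Meier cannulation estimate in an HD subset (Protocol 2.1.2). The documents do not say how procedure failures entered it, so it only shows scale.

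**Step 1. Rate among all in whom the device was introduced**

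ITT rate = AT rate × 150/(150 + F), with failures counted as non-successes.

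| AT rate | F = 10 (factor 0.9375) | F = 5.1 (factor 0.967) |
|---|---|---|
| 60% | 56.3% (−3.8 points) | 58.0% (−2.0) |
| 70% | 65.6% (−4.4) | 67.7% (−2.3) |
| 84.9% | 79.6% (−5.3) | 82.1% (−2.8) |

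With intervals, for 105 successes and F = 10: 105/150 = 70.0% (Clopper-Pearson 62.0% to 77.2%) against 105/160 = 65.6% (57.7% to 72.9%).

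**Step 2. Maturation: the factor is not exactly 150/160**

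SAP 5.2.2 drops AT participants who are not evaluable. With E evaluable AT participants the factor is E/(E + F). If the 10% attrition assumed through 30 days for the safety endpoint applied here (an assumption), E = 135 and the factor is 135/145 = 0.931, slightly lower than 0.9375.

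**Step 3. Cannulation success: how the failures should enter**

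One option is to keep the 10 failures in the Kaplan-Meier risk set without an event. Assume an AT rate of 84.9% at 6 months, 20% attrition by then (Protocol 7.3), constant hazards and failures never censored. Over the 6 months:
- cumulative event hazard a = −ln(0.151) = 1.890
- cumulative censoring hazard g = −ln(0.80) = 0.223
- s = a + g = 2.114
- pooled cumulative hazard = (a/s) × ln[160/(150·e^(−s) + 10)] = 0.894 × ln(160/28.12) = 1.555
- pooled success = 1 − e^(−1.555) = 78.9%

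The product in step 1 gives 79.6%. The pooled curve is lower because censoring removes AT participants while the failures stay, so their share of the risk set grows. Without censoring the two agree at 79.6%. The product (ITT procedure success × AT Kaplan-Meier estimate) avoids this distortion.

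**The case against.** The strongest reply is that the plan openly separates two questions: whether a fistula is created, analysed on ITT in SAP 5.3.1, and how it performs once created, analysed on AT. Both endpoints are timed from creation. SAP 6.1 commits to reporting the numbers of ITT, AT and inserted-but-not-treated participants, so a reader can approximate the correction. Protocol 7.2 says only that AT is the primary population, which leaves room for an ITT analysis. The endpoints are descriptive with no performance goal, and primary safety already uses ITT.

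Most of this stands, and it lowers the importance of the point. It does not supply a planned ITT rate or interval for either endpoint, and the procedure-success result that would let readers make the correction is optional under Protocol 7.6.

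Two stronger readings are tempting. A reader might infer that all secondary effectiveness rates are inflated. The documents do not support that: cumulative functional patency starts at first successful 2-needle use (Protocol 4.2.2), so participants without a fistula do not belong in it. A reader might also infer that every success proportion shrinks by exactly 150/160. That fails because 10 is a planning estimate, maturation drops non-evaluable participants, cannulation success involves censoring, and the exploratory functional maturation and HD usability endpoints are also reported in participants already using two needles, where the factor does not apply.

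**Conclusion.** The point holds for physiological maturation and cannulation success. Their AT rates answer a question conditional on successful creation. As estimates for patients in whom the device is tried, they overstate success by roughly 2 to 5 points for AT rates of 60% to 85%. The lower end rests on about 5 failures (pre-market rate) and the upper end on about 10 (protocol estimate); the actual count could fall outside that range.

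This is a gap in supportive reporting. The AT definition is disclosed, no hypothesis test is affected, and nothing suggests that the failures are concealed. It is worth correcting because the direction is fixed, the outcomes are known and the data will already be in hand.

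**What to change.** Keep AT as the main analysis and add a supportive ITT result, using the ITT definition in Protocol 7.2 and SAP 4.1:

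- **SAP 5.2.2, physiological maturation:** count procedure failures as evaluable participants without the event; report the proportion with a Clopper-Pearson interval beside the AT result.
- **SAP 5.2.3, cannulation success:** report the ITT procedure-success proportion multiplied by the AT Kaplan-Meier estimate, with a delta-method or bootstrap interval. Do not pool the failures into the Kaplan-Meier risk set. State that the product inherits the AT rule that censors permanent abandonment at its date; pooling would instead set failures kept at risk beside abandoned fistulas that are censored, and the result would be hard to interpret.
- **SAP 5.3.1, procedure success:** make the ITT proportion a required result, shown beside these two.
- **SAP 5.3.4 and 5.3.5 (optional):** add the same product row if these exploratory endpoints are reported on the full AT population.

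The cost is a few table rows and a little programming for the product interval. No extra visits, data or participants are needed. The ITT figures will be slightly less favourable than the AT figures.
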